### **11.2. Standard data derivation**

#### **11.2.1. Date derivation**

- SAS date derived from a character date: In case day is missing, 15 is used. In case day & month are missing, 30 June is used.
- Onset day for an event for the mother (AE, medication, vaccination, ...): The onset day is the number of days between the last study vaccination & the onset/start date of the event. This is 0 for an event starting on the same day as a vaccination. See SAS date derived in case the start date of the event is incomplete.
- Onset day for an event for the infant (AE, medication, vaccination, ...): The onset day is the number of days from date of birth of infant & the onset/start date of the event. This is 0 for an event starting on the same day of birth. There could also be events reported in the infant before delivery (anomalies diagnosed during pregnancy at ultrasound investigation), for these cases onset day will be negative '- days. See SAS date derived in case the start date of the event is incomplete.
- Duration: Duration of an event is expressed in days. It is the number of days between the start & the stop dates + 1. Therefore duration is 1 day for an event starting & ending on the same day.

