8.1.5. Pregnancy outcomes

While pregnancy itself is not considered an AE or SAE, any adverse pregnancy outcome or pregnancy complication or elective termination of a pregnancy for medical reasons will be recorded as an AE or a SAE.

The following adverse pregnancy outcomes should always be considered as SAE and will be reported as described in Sections 8.3.1 and 8.3.3:

- Spontaneous pregnancy loss, including:
 - spontaneous abortion, (spontaneous pregnancy loss before/at 22 weeks of gestation).
 - ectopic and molar pregnancy.
 - stillbirth (intrauterine death of foetus after 22 weeks of gestation).

Note: the 22 weeks cut-off in gestational age is based on WHO-ICD 10 noted in the EMA Guideline on pregnancy exposure [EMA, 2006]. It is recognized that national regulations might be different.

- Any early neonatal death (i.e. death of a live born infant occurring within the first 7 days of life).
- Any congenital anomaly or birth defect (as per [CDC MACDP] guidelines) identified in the offspring of a study patient (either during pregnancy, at birth or later) regardless of whether the foetus is delivered dead or alive. This includes anomalies identified by prenatal ultrasound, amniocentesis or examination of the products of conception after elective or spontaneous abortion.

8.2. Detecting and recording adverse events, serious adverse events, pregnancies, pregnancy-related AEs and neonate-related AEs

8.2.1. Time period for detecting and recording adverse events, serious adverse events, pregnancies, pregnancy-related AEs and neonate-related AEs (Amended: 15 July 2015)

All AEs starting within 30 days following administration of each dose of study vaccine/placebo (Day 0 to Day 30) must be recorded into the appropriate section of the eCRF, irrespective of intensity or whether or not they are considered vaccination-related.

The time period for collecting and recording SAEs (including adverse pregnancy outcomes, listed pregnancy-related adverse events of interest/neonate-related adverse events of interest) will begin at the first receipt of study vaccine/placebo and will end at study end (Visit 4) for each subject. See Section 8.3 for instructions on reporting of SAEs.

The time period for collecting and recording AEs, SAEs, pregnancies, pregnancy-related AEs and neonate-related AEs will begin at the first receipt of study vaccine/placebo and will end at study end (Visit 4).

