- The verbatim reports of unsolicited symptoms will be reviewed by a physician and the signs and symptoms will be coded according to MedDRA. Every verbatim term will be matched with the appropriate Preferred Term. The percentage of subjects with unsolicited symptoms occurring within 31 days (Day 0–Day 30) with its exact 95% CI will be tabulated by preferred term. Similar tabulation will be done for Grade 3 unsolicited symptoms and for unsolicited symptoms possibly related to vaccination.
- The percentage of subjects who started to receive at least one concomitant medication (i.e. any medication, antipyretic medication, prophylactic antipyretics) during the 4-day and 31-day follow-up period after vaccination will be tabulated after each dose with exact 95% CI.

- SAEs and withdrawal due to AEs and SAEs following booster dose up to Visit 4 will be described in detail.
- All SAEs assessed as being possibly related to study participation occurring throughout the study period will be described.
- All SAEs assessed as being possibly related to a concurrent GSK medication occurring throughout the study period will be described.
- For the vaccinated household contacts in Spain, SAEs following *Boostrix* vaccination up to 30 days will be described in detail.

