#### **6.4.2. Additional considerations**

- The safety analysis will be performed for each vaccination dose separately ie pregnancy dose and post-delivery dose.
- The percentage of infants with unsolicited symptoms occurring from delivery until 2 months with its exact 95% CI will be tabulated by preferred term. Similar tabulation will be done for Grade 3 unsolicited symptoms and for unsolicited symptoms possibly related to vaccination.
- The summary on concomitant medication (i.e. any medication, antipyretic medication, prophylactic antipyretics) will be performed over the 8 day period instead of 4 days.
- All SAEs will be summarized without distinction of SAEs possibly related to GSK concurrent medication.
- The analysis of safety in the household contacts will be performed on the vaccinated household contacts instead of the Total cohort for household contacts in Spain.

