### 11.2.2. Dose number

- The study dose number is defined in reference to the number of study visits at which injection occurred. More specifically dose 1 refers to all injections administered at the first vaccination visit (Visit 1) while dose 2 corresponds to all injections administered at the second vaccination visit (Visit 3) even if this is the first time a product is administered to the subject.
- Relative dose: the relative dose for an event (AE, medication, vaccination) is the most recent study dose given before an event. In case the event takes place on the day a study dose is given, the related dose will be that of the study dose, even if the event actually took place before vaccination. For instance, if an adverse event begins on the day of the study vaccination but prior to administration of the vaccine, it will be assigned to this dose.
- Relative dose for infant : Since the infants are not receiving any vaccine in this study, relative dose will be '0'.
- The number of doses for a product is the number of time the product is administered to a subject.
- The incidence per dose is the number of vaccination visits at which an event was reported among all vaccination visits.

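### A missing onset day is set to the 15th without regard to the dose date, so an AE in the month of a dose given after the 15th is dated before that dose

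*SAP*

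**What the plan says.** SAP 11.2.1 (Date derivation) gives one rule for incomplete dates: "In case day is missing, 15 is used. In case day & month are missing, 30 June is used". The bullet on maternal events adopts it: "See SAS date derived in case the start date of the event is incomplete". The same bullet defines timing: "The onset day is the number of days between the last study vaccination & the onset/start date of the event".

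SAP 11.2.2 (Dose number) attributes the event: "the relative dose for an event (AE, medication, vaccination) is the most recent study dose given before an event". Its one special case is an event on the calendar day of a dose, which goes to that dose.

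These derived values feed the safety tables. SAP 6.4.1 has "unsolicited symptoms occurring within 31 days (Day 0–Day 30) with its exact 95% CI will be tabulated by preferred term". SAP 6.4.2 adds: "The safety analysis will be performed for each vaccination dose separately ie pregnancy dose and post-delivery dose". Under SAP 11.2.5.1 all vaccinated women stay in the denominator, and a woman without a reported event is treated as not having had it.

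On collection, Protocol 8.2.1 says: "All AEs starting within 30 days following administration of each dose of study vaccine/placebo (Day 0 to Day 30) must be recorded". Protocol 8.1.1 sends conditions present before vaccination to medical history. Neither document limits the imputed date by the dose date.

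**The concern.** For an AE collected after dose 1, the onset is known to be on or after the dose even when the day is missing. A fixed 15th can contradict that. The negative onset day then comes from the imputation alone, yet it decides whether the event is tabulated.

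Dose attribution has the same weakness. In this cross-over, dose 1 and dose 2 are different products for each woman, and the safety tables are split by dose. An event that followed dose 2 but is dated before it is attributed to dose 1. What is at stake is the count of unsolicited AEs, and of newly started concomitant medication, in the Day 0-30 tables.

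**Working it through.** The plan states no figure on this point, so there is none to reproduce. The check applies the SAP rules directly.

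**Inputs.** Missing day = 15, onset day = onset date minus dose date, and attribution to the latest earlier dose (SAP 11.2.1 and 11.2.2); window Day 0-30 (SAP 6.4.1).

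**Formula.** Let the dose fall on day v of a month with L days.
- Onset in the same month: derived onset day = 15 − v, which is negative whenever v > 15.
- Onset in the next month: derived onset day = L + 15 − v, which exceeds 30 when v < L − 15.

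**Examples.**

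| Dose(s) | True onset | Derived onset | Result |
|---|---|---|---|
| Dose 1 on 20 March | 25 March (Day 5) | 15 March | 15 − 20 = Day −5; leaves the table |
| Dose 1 on 20 March | 10 April (Day 21) | 15 April | 31 + 15 − 20 = Day 26; stays in |
| Dose 1 on 10 March | 5 April (Day 26) | 15 April | 31 + 15 − 10 = Day 36; leaves the table |
| Doses on 27 April and 25 May (gap 28) | 27 May | 15 May | Day −10 from dose 2; Day 18 from dose 1: wrong dose |
| Doses on 4 April and 25 May (gap 51) | 27 May | 15 May | Day −10 from dose 2; Day 41 from dose 1: in neither table |
| Doses on 15 April and 10 May (gap 25) | 4 May (Day 19 of dose 1) | 15 May | Day 5 of dose 2: moved forward |

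**Are short gaps realistic?** Vaccination is allowed up to 36 6/7 weeks (Protocol 4.2), and Appendix C puts the expected delivery date at 40 0/7 weeks. For the 33-36 week stratum, delivery on that date comes 280 − 258 = 22 to 280 − 231 = 49 days after dose 1. For a dose at 27 0/7 weeks it is 280 − 189 = 91 days. Dose 2 follows within 72 hours of delivery, so both short and long gaps will occur.

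**How often, among AEs with a missing day?** Assumptions: dose dates uniform over a 365-day year (51% then fall after the 15th), and true onset in Day 0-30 either uniform or exponential with mean 10 or 5 days, truncated at Day 30.

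| Onset pattern | Before own dose, doses after the 15th | Before own dose, all doses | Past Day 30, doses up to the 15th | Past Day 30, all doses |
|---|---|---|---|---|
| Uniform | 26.6% | 13.5% | 22.5% | 11.1% |
| Mean 10 days | 54.0% | 27.4% | 5.7% | 2.8% |
| Mean 5 days | 72.2% | 36.6% | 1.0% | 0.5% |

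The third column is the second times 0.507; for uniform onset, 0.266 × 0.507 = 0.135.

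**Where misdated dose-2 events go.** At gaps of 21 and 28 days, all of them fall inside Day 0-30 of dose 1. At 45 days, only 0.2 of 13.5 percentage points (uniform) or 1.2 of 36.6 (mean 5 days) do. At 60 and 84 days none do, so these events drop out of both tables. In the other direction, 4% to 16% of day-missing dose-1 events move to dose 2 at a 21-day gap, and 1% to 12% at 28 days.

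**The case against.** The strongest reply is that few records are exposed. Diary cards are checked with the woman at Visits 2, 3 and 4 (Protocol 5.6.1.3.9), and omissions found at eCRF review can be queried (Protocol 11.1). Missing days should be uncommon. Solicited symptoms are recorded by day on the diary card. SAEs and the listed pregnancy and neonatal events are reported up to Visit 4, not in a Day 0-30 window. Infant events are counted from birth. The rule is identical in both groups, the secondary safety objectives are descriptive, and the cord-blood analysis does not use AE dates. All of this stands and keeps the point small. It does not make the derived date right where a day is missing.

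A second reply concerns dose 2. SAEs, pregnancy-related and neonate-related AEs are collected continuously from dose 1, and dose 2 follows delivery. Premature labour or antepartum bleeding in the delivery month truly precedes dose 2, so assigning it to dose 1 is correct. This also stands: a correction at dose 2 cannot rest on the calendar month alone.

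Three stronger readings are tempting, and the SAP rules support none of them.
- That every dose after the 15th misplaces its day-missing events. It does not: the onset must also fall in the same calendar month, as the second example shows.
- That the error always takes events from the later dose. Events can also move forward to dose 2 or past Day 30.
- That events are routinely transferred between products. That happens mainly at short gaps; at longer gaps the event is lost from both tables.

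**Conclusion.** The rule is wrong as written for a defined set of records: maternal AEs with a missing onset day, known to have followed a dose, whose month is that of a dose given after the 15th. Each is dated before its own dose. The fixed 15th also pushes some next-month onsets past Day 30 and, at short gaps, moves some dose-1 events to dose 2.

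Under the assumptions above, 13.5% to 36.6% of day-missing AEs are dated before their dose and a further 0.5% to 11.1% fall past Day 30. A lost event understates the rate, because the woman stays in the denominator.

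The effect on the tables cannot be sized, because the documents give no count of partial dates. Purely as an illustration, if 1% to 2% of AEs lacked a day, 0.01 × 0.135 = 0.14% to 0.02 × 0.366 = 0.73% of AEs would be dated before their dose. The consequence is confined mainly to unsolicited AEs and concomitant medication. Nothing here supports inferring a material distortion of the safety conclusions or any effect on the primary result.

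**What to change.** Add to SAP 11.2.1: when a partial onset date is compatible with onset on or after a dose, and the record shows that the event followed that dose (for example, it is on the diary card issued at that vaccination visit), impute no earlier than the dose date and assign the event to that dose. At dose 2, do not apply this to events known to precede delivery or that dose. Use the same wording when the month is also missing, since 30 June has the same gap. List all imputed onset dates with the derived onset day and assigned dose.

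The cost is a condition in the derivation program, one listing, and a check that the eCRF or diary identifies which dose the event followed; the plan describes no dedicated field for this. The downside is that a few events are conservatively placed on Day 0, which also brings them into the Day 0-7 combined tables. The change removes the before-dose error where the record identifies the dose. It does not bring back onsets pushed past Day 30; the listing makes those visible.

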### 11.2.2. Dose number

- The study dose number is defined in reference to the number of study visits at which injection occurred. More specifically dose 1 refers to all injections administered at the first vaccination visit (Visit 1) while dose 2 corresponds to all injections administered at the second vaccination visit (Visit 3) even if this is the first time a product is administered to the subject.
- Relative dose: the relative dose for an event (AE, medication, vaccination) is the most recent study dose given before an event. In case the event takes place on the day a study dose is given, the related dose will be that of the study dose, even if the event actually took place before vaccination. For instance, if an adverse event begins on the day of the study vaccination but prior to administration of the vaccine, it will be assigned to this dose.
- Relative dose for infant : Since the infants are not receiving any vaccine in this study, relative dose will be '0'.
- The number of doses for a product is the number of time the product is administered to a subject.
- The incidence per dose is the number of vaccination visits at which an event was reported among all vaccination visits.

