4.2. Inclusion criteria for enrolment (Amended: 15 July 2015)

Deviations from inclusion criteria are not allowed because they can potentially jeopardise the scientific integrity of the study, regulatory acceptability or subject safety. Therefore, adherence to the criteria as specified in the protocol is essential.

All subjects must satisfy ALL the following criteria at study entry:

Inclusion criteria for study subjects:

- Subjects who, in the opinion of the investigator, can and will comply with the requirements of the protocol (e.g. completion of the diary cards, return for follow-up visits).
- Written informed consent obtained from the subject prior to performing any study specific procedure, as per local regulations.
- A healthy pregnant woman between, and including, 18 and 45 years of age at the time of screening.
- Pregnant subjects at 27^{0/7}-36^{6/7} weeks (completed 27 weeks but not 37 weeks) of gestation at the time of vaccination (Visit 1), as established by ultrasound examination.
- Not at high risk for complications, as determined by the obstetrical algorithm for identification of eligible subjects and the Obstetrical Risk Assessment Form.
- No significant foetal abnormalities, as observed by the level II ultrasound testing conducted after 18 weeks of gestation.
- Nuchal translucency scan, serum testing and any other prenatal tests, if conducted, should suggest normal pregnancy.
- Willing to have the infant born immunised with *Infanrix hexa* and *Prevenar 13*, as per national recommendations, in the follow-up clinical studies DTPA (BOOSTRIX)-048 PRI and DTPA (BOOSTRIX)-049 BST: 048.
- Subjects who do not plan to give their child for adoption or place the child in care.

Inclusion criteria for household contacts in Spain:

- *Household contacts living in the same house as that of the infant.*
- *Household contacts or parent(s)/LAR(s) of the household contacts who, in the opinion of the investigator, can and will comply with the requirements of the protocol (e.g. reporting of SAEs).*
- *Written informed consent obtained from the household contacts or the parent(s)/LAR(s) prior to vaccination, as per local regulations.*
- *Household contacts who are eligible to receive a booster dose of DTP-containing vaccine according to the Summary of Product Characteristics (SmPC) of Boostrix and according to the local governmental recommendations in Spain.*

- ***Female household contacts of non-childbearing potential may be enrolled in the study .***

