In case a woman gives birth to an infant between Visit 1 (Day 0) and Visit 2 (Day 30), the procedures for Visit 2 and Visit 3 will be combined. A blood sample from the mother must be taken before the cross-over vaccination is given to her.

● is used to indicate a study procedure that requires documentation in the individual eCRF.

○ is used to indicate a study procedure that does not require documentation in the individual eCRF.

Pre-vacc: Blood sample to be collected before the dose of the booster vaccination in pregnant women (Visit 1).

Post-vacc: Blood sample to be collected one month after the booster vaccination in pregnant women (Visit 2).

† Father of the child should also sign the informed consent form, if required by the local laws.

* History of all medications, excluding the vitamins and supplements taken by the mother during her pregnancy before receiving the first dose of study vaccine will be recorded in the eCRF.

** Pregnancy screening will include checking of records of ultrasound testing, nuchal translucency scan, serum testing and any other prenatal tests (if performed). Refer to Section 4.2 for details regarding pregnancy screening.

Including adverse pregnancy outcomes and listed pregnancy-related/neonate-related AEs of interest.

§Information will be obtained by interviewing the mother after she agrees to participate in the study. These details can be collected at any of the study visits..

Table 5 List of study procedures for household contacts in Spain

Epoch	Epoch 001				
Type of contact	Screening Visit *	Visit 1	Visit 2	Visit 3	Visit 4
Time-points	Day -14 to 0	Day 0	Day 30	At birth	Post-delivery Month 2
Informed consent		●#			
Check inclusion/exclusion criteria		●#			
Collect demographic data		●#			
Medical history and previous DTP-containing vaccination history		●#			
Urine pregnancy test in female household contacts of child bearing potential		●#			
Pre-vaccination body temperature		●#			
Vaccine administration**		●#			
Recording of administered treatment number		●#			
Recording of serious adverse events (SAEs) and pregnancies †		•	•	•	•
Recording of SAEs related to study participation or to a concurrent GSK medication/vaccine		•	•	•	•

● is used to indicate a study procedure that requires documentation in the individual eCRF.

*Screening visit will not be applicable for household contacts.

**The vaccine for household contacts should be administered only after vaccination of the mother (study subject).

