## 2. STUDY DESIGN

N: Number of subjects planned to be enrolled

Pre-vacc: Blood sample to be collected before the dose of the booster vaccination in pregnant women (Visit 1).

Post-vacc: Blood sample to be collected one month after the booster vaccination in pregnant women (Visit 2).

Protocol waivers or exemptions are not allowed with the exception of immediate safety concerns. Therefore, adherence to the study design requirements, including those specified in the outline of study procedures (Section 5.5 of protocol), are essential and required for study conduct.

- Experimental design: Phase IV, observer-blind, randomised, placebo-controlled, multi-centric, multi-country study with two cross-over groups. All eligible household contacts of the infants born to pregnant women enrolled in Spain will be eligible to receive a single dose of *Boostrix* as part of an assessment of cocooning.
- Duration of the study: The intended duration of the study will be approximately 5 months for each subject.
  - Epoch 001: Booster vaccination starting at Screening visit (Day -14 to 0) and ending at Visit 4 (post-delivery Month 2).

- Study groups: The study groups are defined as follows:
  - dTpa Group: This group will consist of pregnant women who will receive a single dose of *Boostrix* at 27-36 weeks (i.e. completed 27 weeks until 36 weeks) of gestation (Visit 1) and will receive a dose of the placebo post-delivery (within 72 hours).
  - Control Group: This group will consist of pregnant women who will receive a single dose of placebo at 27-36 weeks (i.e. completed 27 weeks until 36 weeks) of gestation (Visit 1) and will receive a dose of *Boostrix* post-delivery (within 72 hours).

The study groups and epoch foreseen in the study are presented in [Table 1](#)

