#### Secondary

- To assess the safety of a single dose of Boostrix in pregnant women, administered during 27-36 weeks of gestation, in terms of the outcomes of pregnancy and listed pregnancy-related adverse events of interest/neonate-related events of interest up to study end (Visit 4).
- To assess the immunogenicity of a single dose of Boostrix administered during pregnancy in terms of seropositivity status for antibodies against pertussis, in the cord blood sample.
- To assess the immunogenicity of a single dose of Boostrix administered during pregnancy in terms of seroprotection/seropositivity status, vaccine response and GMCs for antibodies against diphtheria, tetanus and pertussis, one month post-vaccination.
- To evaluate the reactogenicity of a single dose of Boostrix administered during pregnancy and post-delivery in terms of solicited symptoms during the 8-day (Day 0 – Day 7) follow-up period after vaccination.
- To assess the safety of a single dose of Boostrix administered during pregnancy and post-delivery in terms of unsolicited symptoms during the 31-day (Day 0 – Day 30) follow-up period after vaccination and serious adverse events (SAEs) during the period from Visit 1 up to Visit 4.
- To assess the acceptance rate of a single dose of Boostrix among eligible household contacts of the infants born to pregnant women enrolled in Spain, as part of an assessment of cocooning.
- To assess the safety of a single dose of Boostrix in terms of SAEs among the vaccinated household contacts of the infants born to pregnant women in Spain, as part of an assessment of cocooning, from the day of vaccination till 30 days after the vaccination.

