### Secondary

- Outcome of pregnancy in terms of pregnancy outcomes up to study end (Visit 4).
  - Pregnancy outcomes will include live birth with no congenital anomalies, live birth with congenital anomalies, still birth with no congenital anomalies, still birth with congenital anomalies, elective termination with no congenital anomalies and elective termination with congenital anomalies.
- Outcome of pregnancy in terms of listed pregnancy-related adverse events of interest/ neonate-related events of interest up to study end (Visit 4).
  - Listed pregnancy-related adverse events of interest/ neonate-related events of interest will include gestational diabetes, pregnancy-related hypertension, premature rupture of membranes, preterm premature rupture of membranes, premature labour, premature uterine contractions, intrauterine growth restriction/poor foetal growth, pre-eclampsia, eclampsia, vaginal or intrauterine haemorrhage, maternal death, preterm birth, neonatal death, small for gestational age, neonatal hypoxic ischaemic encephalopathy and failure to thrive/growth deficiency.
- Immunogenicity with respect to components of the study vaccine received during pregnancy, one month post vaccination
  - Anti-D, anti-T, anti-PT, anti-FHA and anti-PRN seroprotection/seropositivity status and antibody concentrations.
  - Vaccine response to PT, FHA and PRN. Refer to section [11.2.4](#)
  - Vaccine response to anti-D and anti-T. Refer to section [11.2.4](#)
- Immunogenicity with respect to components of the study vaccine, in the cord blood sample.
  - Anti-PT, anti-FHA and anti-PRN seropositivity status.
- Solicited local and general symptoms (at Visit 1 and Visit 3).
  - Occurrence of each solicited local/general symptoms during the 8-day (Day 0- Day 7) follow-up period after the vaccination.
- Unsolicited adverse events (at Visit 1 and Visit 3).
  - Occurrence of unsolicited AEs within 31 days (Day 0 – Day 30) after any vaccination, according to the Medical Dictionary for Regulatory Activities (MedDRA) classification.
- Serious adverse events (SAEs).

- Occurrence of serious adverse events from Dose 1 up to study end (Visit 4).
- Percentage of household contacts of the infants born to pregnant women vaccinated in Spain who accepted *Boostrix* vaccine as part of an assessment of cocooning among the eligible household contacts.

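### When the post-delivery dose falls within 30 days of the pregnancy dose, the SAP cuts short the 31-day pregnancy-dose window in both groups without changing the denominator

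*SAP*

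**What the plan says.** **Timing.** Protocol 4.2 allows Dose 1 from 27 weeks 0 days to 36 weeks 6 days. SAP section 2 states that a woman in the dTpa Group "will receive a dose of the placebo post-delivery (within 72 hours"); a Control woman receives Boostrix at that point. Protocol Table 6 gives no Visit 1 to Visit 3 interval. The note to Protocol Table 4 foresees early delivery ("In case a woman gives birth to an infant between Visit 1 (Day 0) and Visit 2 (Day 30")), combines the two visits, and still has the cross-over dose given. Table 6 removes a woman who delivers before 21 days from the ATP immunogenicity cohort only, so she stays in the safety analysis.

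**Window.** The secondary endpoint in SAP section 4 is "Occurrence of unsolicited AEs within 31 days (Day 0 – Day 30) after any vaccination", and Protocol 8.2.1 collects events over that period after each dose. SAP section 3 sets the matching objective for Boostrix given in pregnancy and post-delivery.

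**Attribution.** For mothers, SAP 11.2.1 says: "The onset day is the number of days between the last study vaccination & the onset/start date of the event". SAP 11.2.2 adds that "the relative dose for an event (AE, medication, vaccination) is the most recent study dose given before an event", and an event on the day of Dose 2 goes to Dose 2 even if it began before the injection.

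**Tabulation.** SAP 6.4.2 says: "The safety analysis will be performed for each vaccination dose separately ie pregnancy dose and post-delivery dose". In SAP 11.2.5.1 the denominator for unsolicited symptoms and concomitant medication is every vaccinated woman, and SAP 11.2.6 treats a woman with no report as free of the event. Neither document has a rule for overlapping windows, censoring or person-time.

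**The concern.** The plan promises a 31-day percentage after the pregnancy dose. For a woman whose Dose 2 comes on Day 22, the derivation delivers Days 0 to 21. Anything she reports on Days 22 to 30 is re-dated as Days 0 to 8 after Dose 2 and leaves the pregnancy-dose table, while she still counts as a woman observed for the whole window. A percentage built this way can only stay the same or fall.

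The post-delivery tables are affected too. In the dTpa Group, the placebo column includes days that are still within 31 days of Boostrix. That column is the only randomised reference for post-delivery Boostrix.

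Women dosed at 33 to 36 weeks are the most exposed. That range is a minimisation category and a planned immunogenicity subgroup, so late dosing is an intended part of enrolment. The protocol justifies the trial partly by the limited safety data for this vaccine in pregnancy, so pregnancy-dose percentages ought to match their label.

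**Working it through.** The plan states no figure for dose overlap, so there is none to reproduce.

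**1. Calendar arithmetic.** Let t be the study day of Dose 2:

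t = (gestational age at delivery − gestational age at Dose 1, in days) + k, with k = 0 to 3 for the 72 hours.

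The windows overlap if t ≤ 30. Dose 1 keeps t of its 31 days (Day 0 to Day t − 1), and 31 − t days move to Dose 2.

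- Dose 1 at 36w6d, delivery at 40w0d: 280 − 258 = 22, so t = 22 to 25 and 6 to 9 days move.
- Dose 1 at 36w0d, delivery at 39w0d: 273 − 252 = 21, so t = 21 to 24 and 7 to 10 days move.
- Dose 1 at 35w0d, delivery at 39w0d: 273 − 245 = 28, so t = 28 to 31 and 0 to 3 days move.

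**2. One fixed delivery age.** Assume Dose 1 is spread evenly over the 70 eligible days (27w0d to 36w6d) and count the dosing days with t ≤ 30. The range covers k = 3 to k = 0.

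| Delivery | Overlapping dosing days of 70 | Share | Of 340 per group |
|---|---|---|---|
| 37w0d | 27 to 30 | 39% to 43% | 131 to 146 |
| 38w0d | 20 to 23 | 29% to 33% | 97 to 112 |
| 39w0d | 13 to 16 | 19% to 23% | 63 to 78 |
| 40w0d | 6 to 9 | 9% to 13% | 29 to 44 |
| 41w0d | 0 to 2 | 0% to 3% | 0 to 10 |

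**3. A spread of delivery ages.** Assumptions:

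- Dosing is even over the eligible range.
- Delivery age is normal, with an SD of 1.6 to 2.0 weeks, among women undelivered at dosing.
- Preterm delivery is 11.7% (the planning rate in Protocol Table 17) or 5%. The lower value is assumed because Protocol 4.2 and 4.3 exclude high-risk pregnancies.
- Dose 2 is spread evenly over 0 to 3 days after delivery.

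The mean delivery age is 37 + z × SD, with z = 1.645 for 5% and 1.19 for 11.7%. For example, 37 + 1.645 × 2.0 = 40.29 weeks and 37 + 1.19 × 1.6 = 38.90 weeks. Simulation gives:

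| Preterm | SD (weeks) | Women with overlap | Of 340 | Of those dosed from 33 weeks | Dose 1 window days moved |
|---|---|---|---|---|---|
| 5% | 2.0 | 13.1% | 44.5 | 31.5% | 4.2% |
| 5% | 1.6 | 16.9% | 57.5 | 41.3% | 5.4% |
| 11.7% | 2.0 | 19.3% | 65.7 | 45.5% | 7.0% |
| 11.7% | 1.6 | 22.9% | 78.0 | 55.0% | 8.3% |

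Affected women lose about 10 to 11 of 31 days. The last column follows: 0.131 × 10.0 / 31 = 4.2% and 0.229 × 11.2 / 31 = 8.3%. Dose 2 falls within 7 days of Dose 1 in about 1% to 2% of women, so solicited symptoms are barely touched.

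**The case against.** **The rule is a recognised convention and applies to both groups.** This stands. Allocation is 1:1 and minimised on gestational age (27-32 and 33-36 weeks), so truncation should be similar in the two groups. A reader might infer that Boostrix reactions are being hidden under placebo and that the Dose 1 comparison therefore favours Boostrix. The documents do not support that. Control women lose the same late days, and the moved events are of any cause, mixed with the puerperium.

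**The scope is narrow.** This largely stands. Pregnancy outcomes and listed events of interest are tabulated by group up to Visit 4, and infant events have relative dose 0, so none of these move. SAEs are described in detail up to Visit 4. What remains is mainly non-serious unsolicited events and 31-day medication. The secondary objectives are descriptive and no within-woman cross-over comparison is planned, so the absence of a wash-out is not itself a flaw.

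**An analysis after any vaccination would count these events once by group.** This is only a partial answer. The endpoint and one mock table title use that wording, but SAP 6.4.2 requires analysis by dose, and SAP section 12 describes the mock tables as illustrations copied from other studies.

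**The obvious remedy could do harm.** This stands and shapes the fix. Counting every event to Day 30 of Dose 1 whether or not Dose 2 has been given would put the first days after Boostrix into the Control Group's placebo column. That could raise the control rate and mask an excess. The present rule avoids this.

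**Conclusion.** The point holds as a mismatch between the stated 31-day window and what the derivation delivers. In both groups, pregnancy-dose percentages for unsolicited events and concomitant medication are understated, and the post-delivery tables carry events from inside the Dose 1 window. Neither a directional bias in the Dose 1 comparison nor vaccine causation of the moved events follows.

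The size is about 13% to 23% of women, or about 45 to 78 of 340 per group, and about 4% to 8% of all Dose 1 window days. Even dosing, the normal shape, the SD and the 5% preterm rate are assumptions. With a single fixed delivery age the share runs from almost none at 41 weeks to about 40% at 37 weeks. The share of days approximates the share of events lost only if onsets are even over the window; clustering around delivery would change it.

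This is worth correcting because it is cheap and the data are already collected. It does not threaten the primary objective.

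**What to change.** In SAP 6.4.2, 11.2.1 and 11.2.2:

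- Keep the most-recent-dose rule for the main tables, but label the Dose 1 tables as events up to Day 30 or Dose 2, whichever comes first.
- Report by group the number of women with fewer than 31 days between doses, and the Dose 1 follow-up days.
- Add sensitivity versions of the Dose 1 and post-delivery tables for unsolicited events and medication, limited to women with at least 31 days between doses. For Dose 1, person-time rates censored at Dose 2 would also serve.
- Optionally, add a supportive table for the dTpa Group alone that counts all events on Days 0 to 30 from Dose 1 regardless of Dose 2. It should not replace the main Dose 1 comparison.

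The cost is SAP wording, programming and a few extra tables. The restricted set under-represents women dosed late or delivering early, so it supplements the main tables and should carry a footnote saying so. No change to dosing, visits or data collection is needed.
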